1. PURPOSE OF THE STUDY

a. Brief Summary

This study is designed to examine three treatment conditions for traumatized youth: Cue-Centered Treatment (CCT), Trauma-Focused Cognitive-Behavioral Therapy (TF-CBT), and Treatment as Usual (TAU) to determine which treatment works most effectively for which youth. We would like to determine feasibility of training on the treatment interventions. In addition, this study aims to inform development of systems of care for chronically traumatized youth.

Objectives

We hope to determine whether 1) TF-CBT and CCT will have better outcomes than TAU, 2) Child characteristics predict better outcome in either TF-CBT or CCT and to identify which phases of treatment are most effective, and 3) Imaging findings will be predictors of improved outcome. This research is important because while there are many existing trauma interventions for youth, little is known about what is most essential in those interventions. This study will shed light on what components of treatment are most effective. Furthermore, there are minimal guidelines on how to select the most appropriate intervention for a particular child. This study will contribute to that knowledge by informing which interventions are suited best for which youth.

b. Rationale for Research in Humans

This project will allow the investigation of three existing treatment interventions for children with post-traumatic stress disorder. The purpose is to inform treatment selection based on most effective treatment components and child characteristics.

2. STUDY PROCEDURES

a. Procedures

The children will be referred from Stanford Youth Solutions and UCSF CAS. UCSF has approved recruitment at their site and they have provided their own consent forms. Some children may also be self-referred from the community as a response to a flyer that may have been distributed to them in a public forum, from a community organization, from a physician/pediatrician, or a hospital setting.

School staff will speak with parents of children they have identified as potential study candidates and with verbal consent will submit parent's name and phone number so that the research coordinator can make contact directly to conduct phone screening. School staff may also obtain verbal consent for a Stanford research team member to come to the school site and do informed consent process and screening at school for any participants that may have

transportation barriers.

Caregivers will undergo a telephone or in-person screening according to the inclusion and exclusion criteria. Written consent for participation will be obtained from participants, parents and/or legal guardians. Participants will be randomly assigned to one of three treatment conditions: TF-CBT, CCT, or TAU. Assessments will be administered at 4 time points: 1) pre-treatment, 2) mid-therapy, 3)post-treatment, and 4) three month follow-up. A medical/developmental history form will be completed only pre-treatment. The vocabulary and block design subtests of the Wechsler Abbreviated Scale of Intelligence (WASI-II) will be administered only pre-treatment to rule out potential confounds for neuroimaging. The UCLA PTSD Reaction Index (PTSD-RI) parent and child versions will be used to assess exposure to traumatic events and posttraumatic stress symptoms. Given that trauma has high comorbidity with depression and anxiety disorders these symptoms will be assessed using the Multidimensional Anxiety Scale for Children (MASC), Children's Depression Inventory (CDI), and Trauma Symptom Checklist for Children (TSCC) or Trauma Symptom Checklist for Young Children (TSCYC). Executive functioning will be assessed by both child and parent report using the Behavioral Rating Inventory of Executive Function (BRIEF) and the Brief Impairment Scale (BIS) for the parent. A post-treatment services form will be completed only at the three month follow up appointment.

In addition, functional near-infrared spectroscopy (fNIRs) will be conducted at each of these time points to assess tasks of working memory, response inhibition, and facial recognition. We will be using the NIRScout which is a portable NIRS recording unit. NIRS technology uses specific wave lengths of light, introduced at the scalp, to enable the noninvasive measurement of changes in the relative ratios of deoxygenated hemoglobin (deoxy-Hb) and oxygenated hemoglobin (oxy-Hb) in the capillary beds during brain activity.

The collaborating institutions roles will be for [name] of Drexel University to provide weekly case consultation via phone for the TF-CBT therapists as well as evaluate audio recordings for fidelity. [name] of Iowa State University will serve as a consultant for statistical analyses. [name] of Serving Children and Adults in Need, Inc. will evaluate Spanish audio recordings for fidelity.

b. Procedure Risks

The current research design poses minimal risk to the participants. All participants will be closely monitored for any adverse events that may arise from the study. All participants will be assisted in obtaining further treatment if needed.

c. Use of Deception in the Study

N/A

d. Use of Audio and Video Recordings

Audio recordings will be made of every treatment session for each of the three study interventions for the purposes of intra and inter rater reliability, if consent is given. These recordings will be identified only by subject number, will be kept in a locked file cabinet, and in a locked office. Only research staff on this project will have access to this data. Anonymity of all participants will be maintained throughout. If caregiver consent is provided, the audio recordings may be used in scientific meetings. The recordings will be destroyed after completion of the study.

Audio for participants at SYS will be recorded using encrypted, password protected recording devices owned by Stanford University. Recording devices at SYS have already been approved for use since the launch of the study. New iPads are being introduced to be used to audio record therapy sessions at the UCSF site. Stanford has purchased 3 iPads for their use. These iPads have gone through the attestation process and are fully compliant to be used with PHI by Stanford University. All devices and iPads are kept locked, are secure and password-protected. All audio files are uploaded and stored in MedBox, and then deleted from the devices.

e. Alternative Procedures or Courses of Treatment

Other forms of psychotherapy or psychopharmacology may be advantageous to participants. However, there is no strong evidence to suggest that these treatments are necessarily better than the interventions that participants will be receiving.

f. Will it be possible to continue the more (most) appropriate therapy for the participant(s) after the conclusion of the study?

Yes.

g. Study Endpoint(s)

The study is scheduled to end by July 2020. On average, each individual will actively participate for three to four months. If one study intervention clearly proves to be more effective than another during the course of the study then the study will be terminated before the projected total number of participants has been enrolled and we will make that intervention available to all participants.

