k. Payments to Participants

Participants who complete all behavioral assessments and fNIRs at each time phase will receive a \$25 gift card (a total of \$100) which will incentivize participants to complete the assessments.

l. Costs to Participants

There are no costs to the participant.

m. Planned Duration of the Study

The entire duration of the study will be 4.5 years ending in July 2020.

- (i) 10-15 minutes for screening of participants
- (ii) 15-18 weekly 45-minute treatment sessions over the duration of 3 months. There will be completion of 3 hour behavioral assessments over 4 time points (pre-, mid-, post-treatment and six month follow-up). Participants will also do 45-60 minutes of fNIRs imaging at each of the time points.
- (iii) Participant data will be processed and analyzed per participant, but mostly in bulk. Participant data will be analyzed periodically throughout the length of the study. After data acquisition, data will be checked for quality and will be double-entered. Analysis will be within and between groups.

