b. International Research Risk Procedures

N/A

c. Procedures to Minimize Risk

Confidentiality will be maintained by using designated therapy rooms at SYS (including for community-referred youth) and UCSF CAS and assigning participants a coded number by which all their data will be identified.

For school-referred youth, therapy may be provided at their respective school site in designated rooms for confidential therapy sessions. These rooms are already being used by school psychologists and social workers and will be made available for us to minimize any potential transportation barriers for participants.

Evaluation of the participants will occur at three time points during the treatment and if any hazards are detected such as co-morbid psychological symptoms, the study therapists will provide appropriate referrals to community resources.

d. Study Conclusion

The study will terminate in July 2020, after all 135 participants have completed treatment.

Regular evaluations during four time points (pre-, mid-, post- treatment, and 3 month follow-up) will facilitate identification of any adverse effects. If participants have clinically significant worsening of PTSD, anxiety, or depressive symptoms, suicidal or violent behaviors, or substance dependence therapy will be discontinued. The study therapists, all masters level clinicians, will be able to make community referrals if they determine further intervention is warranted. Adverse effects and specific stopping triggers will be reported to the IRB.

e. Data Safety Monitoring Plan (DSMC)

i. Data and/or events subject to review

N/A

ii. Person(s) responsible for Data and Safety Monitoring

N/A

iii. Frequency of DSMB meetings

N/A

iv. Specific triggers or stopping rules

N/A

v. DSMB Reporting

N/A

vi. Will the Protocol Director be the only monitoring entity? (Y/N)

Yes.

vii. Will a board, committee, or safety monitor be responsible for study monitoring? (Y/N)

No.

f. Risks to Special Populations

Research not involving greater than minimal risk. The research must present no greater than minimal risk to children and adequate provisions must be made for soliciting the assent of the children and the permission of their parents or guardians. Please provide rationale for the above statement.

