# Child Characteristics, Neuromarkers, and Intervention Components Impacting Treatment Outcome: CCT, TF-CBT, TAU

NCT02926677

9/18/20

[name], Principal Investigator  
Stanford University  
Stanford, California 94305

Planned Sample Size: Analyses will be conducted on data for participants that completed treatment from baseline to month 3 (end of treatment). The sample size is 8 participants for the CCT group, 8 for TF-CBT, and 6 for TAU.

Planned Analyses: Factorial ANOVAs comparing baseline to month 3 (end of treatment) total scores on all outcome measures (UCLA PTSD Reaction Index for DSM 5 child and parent versions, Child Depression Inventory, Multidimensional Anxiety Scale for Children, Behavior Rating Inventory of Executive Function) will be conducted for each treatment arm.

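### The SAP analyses only baseline and month 3 in treatment completers, so early change, late change and durability cannot be estimated although four assessments are scheduled

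*Protocol*

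**What the plan says.** The protocol, section 2.a, sets the schedule: "Assessments will be administered at 4 time points: 1) pre-treatment, 2) mid-therapy, 3)post-treatment, and 4) three month follow-up". Section 6.d repeats it: "Regular evaluations during four time points (pre-, mid-, post- treatment, and 3 month follow-up) will facilitate identification of any adverse effects". Imaging follows the same calendar; section 2.a adds that "functional near-infrared spectroscopy (fNIRs) will be conducted at each of these time points". Section 5.m also lists four visits but gives the last one a different date: "pre-, mid-, post-treatment and six month follow-up".

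Section 1.a makes it part of objective 2 "to identify which phases of treatment are most effective".

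The SAP names one analysis: "Factorial ANOVAs comparing baseline to month 3 (end of treatment) total scores on all outcome measures". Its sample-size paragraph limits this to treatment completers, 8 in CCT, 8 in TF-CBT and 6 in TAU. Month 3 is labelled there as the end of treatment, so it is the post-treatment visit and not the three-month follow-up. Mid-therapy and follow-up scores are given no role, and nothing is said about children who did not complete.

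**The concern.** Two features of the SAP act together. It uses two of the four visits, and it keeps only children who completed treatment.

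The first leaves the phase question without an analysis. Mid-therapy is the only scheduled assessment inside the treatment period, so it is the only one that can separate earlier from later change. Follow-up is the only evidence on whether gains last.

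The second means that a child who gave pre-treatment and mid-therapy scores and then left contributes neither. Selecting on completion also departs from the randomised comparison: if leaving is related to symptoms or to arm, the completers' contrast is biased. Adding visits while keeping the completer restriction would not recover those children, so both features have to change.

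**Working it through.** **Inputs.** Four visits (protocol 2.a, 6.d); two visits analysed and 8, 8 and 6 completers (SAP); planned enrolment 135 (protocol 5.a). The documents give no alpha, power, effect size, standard deviation, dropout rate or correlation between visits, and the SAP derives no sample size, so there is no figure of the plan's own to reproduce.

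**Scores used.** 8 + 8 + 6 = 22 completers. With complete data, 4 × 22 = 88 scores per measure; the SAP uses 2 × 22 = 44, or 50%. Protocol 5.m puts each visit at 3 hours of behavioural assessment plus 45–60 minutes of imaging, so the two unused visits cost a fully assessed child 2 × 3.75 to 2 × 4 = 7.5 to 8 hours.

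**What can be estimated.** Within an arm, write the mean scores as pre, mid, post and fu. The targets are early change (mid − pre), late change (post − mid) and maintenance (fu − post). The SAP observes only pre and post. Add any constant k to mid: pre and post are unchanged, early change rises by k and late change falls by k. The data analysed cannot distinguish these cases. The fu mean never enters. A rank check gives the same answer: none of the three contrasts is estimable from two visits, and all three are from four. This step needs no assumption.

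**What early leavers could add.** Take 8 completers in an arm plus m children with pre and mid scores only. Assume scores missing at random, unit variance at each visit, and correlation r of 0.5 or 0.7, either equal between all visits or decaying (r between adjacent visits, r² between pre and post). With generalised least squares, the variance of a change relative to completers only is

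ratio = s + (1 − s) × 8/(8 + m),

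where s is the share of the change's variance that is residual in post given pre and mid. Two examples for pre to post at r = 0.5:

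- Equal correlation: residual 1 − 2 × 0.25/1.5 = 0.667; change variance 2 × (1 − 0.5) = 1; s = 0.667. At m = 2, 0.667 + 0.333 × 0.8 = 0.93.
- Decaying: residual 1 − 0.25 = 0.75; change variance 2 × (1 − 0.25) = 1.5; s = 0.5. At m = 2, 0.5 + 0.5 × 0.8 = 0.90.

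For pre to mid, s = 0. Over the four correlation settings:

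| m per arm | Pre to mid | Pre to post | Mid to post |
|---|---|---|---|
| 0 | 1.00 | 1.00 | 1.00 |
| 2 | 0.80 | 0.90–0.94 | 0.93–0.97 |
| 4 | 0.67 | 0.83–0.90 | 0.89–0.95 |
| 8 | 0.50 | 0.75–0.85 | 0.83–0.93 |

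**How precise a phase contrast would be.** For early change in CCT (8) against TAU (6), the variance of one child's change is 2 × (1 − r): 1.0 at r = 0.5 and 0.6 at r = 0.7. With 1/8 + 1/6 = 0.2917, the standard error is √0.2917 = 0.54 or √(0.6 × 0.2917) = 0.42 SD. Multiplying by 2.179 (t, 12 degrees of freedom) gives 95% half-widths of about 1.18 and 0.91 SD.

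**The case against.** The strongest defence is that 22 children support only a simple comparison, and that baseline to month 3 is a reasonable main one. That stands: month 3 can remain the main contrast, and phase results at this size are descriptive. It does not explain why a stated objective has no analysis and no statement that it was dropped. Protocol 5.m says that data will be analysed periodically, within and between groups, but it names no visit or model and does not fill the gap.

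Three stronger readings are tempting, and the documents support none of them.

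- A reader might take 135 − 22 = 113 as children who dropped out. But 135 is planned enrolment. Neither document says how many were enrolled or randomised, or how many left early, and protocol 6.d expects all 135 to complete treatment. The gap may be largely children never recruited.
- A reader might conclude that usable mid-therapy scores were in fact thrown away. The completer rule makes this possible, but no passage shows that any early leaver had such a score. If none did, the m = 0 row applies.
- A reader might think that modelling the mid-therapy visit would settle which phases work best. One visit splits treatment into two halves, and half is confounded with elapsed time. The documents do not map CCT or TF-CBT phases to that visit. It is necessary for the objective, not sufficient.

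The protocol's schedule is not itself at fault. The defect lies in the SAP.

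**Conclusion.** The point holds. Under the SAP, early change, late change and durability are not estimable, and half of the scores scheduled in the 22 completers have no planned use. This part rests on the schedule and the SAP's wording alone.

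The loss from early leavers is conditional. Where they have mid-therapy scores, leaving them out costs precision and risks attrition bias. The size is unknown: 2 to 8 such children per arm would lower the variance of the baseline-to-month-3 change by about 6% to 25%, and few or none would change it little or not at all. Those figures assume 8 completers per arm, correlations of 0.5 to 0.7 and scores missing at random. Even with no gain in precision, the early, late and follow-up contrasts become estimable once all visits are modelled.

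**What to change.** Replace the SAP's planned analysis as follows.

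- For each outcome, fit a repeated-measures mixed model to all available scores from all randomised children, with arm, visit and arm-by-visit, and small-sample degrees of freedom. Include any post-treatment or follow-up scores from children who stopped therapy.
- Treat baseline either as an outcome, with means constrained equal across arms, or as a covariate for the later visits, not both.
- Keep the month-3 arm contrast as the main result.
- Report baseline-to-mid and mid-to-post change by arm, each contrasted with TAU over the same interval, with confidence intervals and labelled exploratory.
- Report the follow-up contrast after reconciling protocol 2.a and 6.d (three months) with 5.m (six months).
- State the numbers randomised and the numbers observed at each visit, by arm.
- Label the change as a dated SAP revision. The SAP is dated 9/18/20, after the planned July 2020 end of the study, so readers need to see when the method was set.

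If the sponsor prefers to keep the two-visit analysis, the SAP should say that the phase objective is not addressed.

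The cost is some analysis work and more parameters in a very small sample; no new data collection is needed. With baseline constrained, there are 1 + 3 × 3 = 10 means, and an unstructured covariance over four visits adds 4 × 5/2 = 10 parameters. A simpler covariance should therefore be named in advance in case that one cannot be fitted. The model relies on scores being missing at random, so it reduces the risk of attrition bias and does not remove it.

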3. BACKGROUND

a. Past Experimental and/or Clinical Findings

A previous RCT of CCT (Carrion et al., 2013), sought to examine the efficacy of the intervention as a short-term, manual-based intervention for youth in the school setting with interpersonal violence exposure undergoing concurrent and chronic environmental adversity. The study findings, published in the Journal of Traumatic Stress (Carrion et al., 2013), utilized hierachal linear modeling analyses to show that compared to the waitlist group, the cue-centered treatment group had greater reductions in PTSD symptoms both by caregiver and child report, as well as caregiver anxiety. Cue-centered treatment, a hybrid trauma intervention merging diverse theoretical approaches, demonstrated feasibility, adherence, and efficacy in treating youth with a history of interpersonal violence.

The previous RCT proved the efficacy of CCT compared to a waitlist group. The next step therefore, is to compare CCT to an active treatment which we chose to be TF-CBT due to the numerous RCTs proving the efficacy of TF-CBT in reducing trauma and associated symptoms. However, about 20-30% of youth do not respond to cognitive-behavioral therapies.

b. Findings from Past Animal Experiments

N/A

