5. PARTICIPANT POPULATION

a. Planned Enrollment

135 participants between 7 and 18 years of age and 135 caregivers (one caregiver for each participant). Participants will be enrolled at SYS in Sacramento (not Stanford-affiliated) and at UCSF CAS in San Francisco (not Stanford-affiliated). These will be trauma exposed youth presenting with posttraumatic stress symptoms and their caregivers as this is the target population for CCT and TF-CBT.

b. Age, Gender, and Ethnic Background

Youth ages 7-18 will be recruited for the study of all genders and ethnic backgrounds.

c. Vulnerable Populations

This study involves vulnerable subjects as we aim to study the effectiveness of several interventions for traumatized youth. 135 youth will be under treatment with therapists trained in assessment and treatment of traumatized youth. They will evaluate participants to determine if they need additional resources. We will provide referrals to those resources and work closely with SYS and UCSF CAS to ensure they are provided and SYS and UCSF CAS also have additional supportive services to which participants may be referred. For those youth that are community-referred, our research staff and therapist will provide the participants with any appropriate resources necessary.

d. Rationale for Exclusion of Certain Populations

N/A

e. Stanford Populations

N/A

f. Healthy Volunteers

N/A

g. Recruitment Details

Potential participants will be identified by the therapists at SYS and by staff at UCSF CAS. A designated contact person at each site will verify that potential participants agree to be contacted for screening by the research coordinator/UCSF designated staff. The study coordinator/UCSF designated staff will only then conduct a phone or in-person interview with potential participants' legal guardians to assess inclusion/exclusion criteria. If qualified participants and their legal guardians consent, they will be enrolled in the study.

Potential participants may also be identified via responses to flyers posted in community centers and public forums. Additionally, flyers, letters, and supplemental informational guides will be sent to physicians/pediatricians, schools, and community organizations to distribute to any patients or students that may be identified as potential participants.

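### The overall CCT versus TF-CBT comparison that motivates the trial is not a numbered objective, and the SAP gives it no between-arm estimate or confidence interval

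*Protocol*

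**What the plan says.** Protocol section 3.a reports that CCT outperformed a waitlist in an earlier randomised trial, and continues: "The next step therefore, is to compare CCT to an active treatment which we chose to be TF-CBT". It gives as the reason that TF-CBT already has support from many randomised trials.

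Protocol section 1.a states the general aim as "to determine which treatment works most effectively for which youth". The first two numbered objectives ask whether "1) TF-CBT and CCT will have better outcomes than TAU, 2) Child characteristics predict better outcome in either TF-CBT or CCT". The second also covers phases of treatment, and the third concerns imaging predictors. None states an overall CCT versus TF-CBT contrast.

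Protocol section 2.a sets up the arms: "Participants will be randomly assigned to one of three treatment conditions: TF-CBT, CCT, or TAU". No allocation ratio is given.

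The SAP's sample-size paragraph restricts analysis to treatment completers: "The sample size is 8 participants for the CCT group, 8 for TF-CBT, and 6 for TAU". Its analysis paragraph plans factorial ANOVAs of baseline against month 3 total scores on each outcome, to be run for each arm. It names no contrast between arms, no effect estimate, no confidence interval, no margin and no significance level.

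**The concern.** The comparison that justifies the trial has no defined quantity in the analysis plan. If the ANOVAs are run arm by arm, the report will contain three separate before-and-after results. Readers will set the CCT result beside the TF-CBT result, because the background has told them that this is the question. Improvement in both arms does not show that the therapies perform alike, and significance in one arm but not the other does not show that they differ. Only an estimate of the difference, with its uncertainty, addresses the question. Because TF-CBT is presented as the established treatment, apparent parity would carry weight that data from 16 children cannot bear.

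**Working it through.** **Where the comparison appears**

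| Place | What it says about CCT and TF-CBT |
|---|---|
| Protocol 3.a | Overall head-to-head is the next step |
| Protocol 1.a, general aim | Which treatment suits which child |
| Protocol 1.a, objective 1 | Each therapy against TAU |
| Protocol 1.a, objective 2 | Child characteristics predicting outcome in either therapy |
| Protocol 2.g | One intervention might prove more effective than another; no contrast or threshold |
| Protocol 5.m | Within- and between-group analysis; no contrast named |
| SAP, planned analyses | Baseline against month 3, for each arm |

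**Inputs.** From the SAP: CCT 8, TF-CBT 8, TAU 6, so 8 + 8 + 6 = 22 analysed. From protocol section 5.a: 135 youth planned. The 135 cannot be reproduced, because no significance level, power, effect size, SD, margin or dropout rate is given. I assume a two-sided 0.05 level (one-sided 0.025 for non-inferiority) and work in SD units of the analysed score.

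**Precision of CCT minus TF-CBT, unadjusted.** Half-width of the 95% interval = t(0.975, n1+n2−2) × √(1/n1 + 1/n2).
- 8 versus 8: 2.145 × √(1/8 + 1/8) = 2.145 × 0.5 = 1.07 SD.
- 45 versus 45, if the 135 were allocated equally (135/3 = 45): t(0.975, 88) × √(2/45) = 0.42 SD.

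**With baseline adjustment.** Multiply by √(1 − r²), where r is the assumed correlation of baseline with month 3. This ignores the one degree of freedom spent on the covariate.
- r = 0.3: 1.072 × 0.954 = 1.02 baseline SD.
- r = 0.5: 1.072 × 0.866 = 0.93.
- r = 0.7: 1.072 × 0.714 = 0.77.

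**Why within-arm results do not substitute.** With 8 children, a mean change is significant at 0.05 when it exceeds t(0.975, 7)/√8 = 2.365/2.828 = 0.84 SD of the change score. The following changes are invented for illustration, with equal SDs.
- Changes of 0.9 and 0.8 SD: one arm is significant and the other is not, yet the difference is 0.1 SD with interval 0.1 ± 1.07, or −0.97 to 1.17.
- Changes of 0.9 and 1.9 SD: both arms are significant, yet they differ by 1.0 SD with interval −0.07 to 2.07.

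In neither case does the pattern of within-arm significance describe the difference.

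**Non-inferiority, for scale.** No margin is stated, so a range is assumed, with the true difference zero.

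| Margin (SD) | Power, 8 per arm | Power, 45 per arm | n per arm for 80% power |
|---|---|---|---|
| 0.2 | 6% | 15% | 393 |
| 0.3 | 8% | 29% | 175 |
| 0.4 | 11% | 47% | 99 |
| 0.5 | 15% | 65% | 63 |
| 0.8 | 32% | 96% | 25 |

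**The case against.** The best defence is that the protocol does address the two therapies together. The general aim and objective 2 ask which child does better in which therapy. Section 2.g contemplates one intervention proving more effective than another, and section 5.m promises between-group analysis. The word factorial in the SAP could also cover an arm-by-time term. This stands in part: it would be wrong to say that the objectives ignore CCT versus TF-CBT. But a moderator question is not the overall contrast, and none of these places defines one. An arm-by-time term would be a joint test across three arms, not an estimate of CCT minus TF-CBT.

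A reader might infer more: that the trial plans a test of 8 against 8 children and will present a non-significant result as showing that CCT is as good as TF-CBT. The documents do not support that. The SAP names no such test, and neither document proposes or prepares an equivalence or non-inferiority claim. That misreading is foreseeable, but it is not planned.

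A reader might also infer from the half-width that no margin could be met. That is too absolute. Meeting a margin depends on the observed difference as well as the half-width, and the chance is 32% at a 0.8 SD margin if the therapies are truly equal.

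**Conclusion.** The point holds as a gap between rationale and analysis. The overall CCT versus TF-CBT comparison is put forward as the trial's next step, but it is absent from the numbered objectives and has no between-arm estimate in the SAP. The textual finding needs no assumption beyond the natural reading of the SAP's ANOVAs as arm by arm. If an arm-by-time term is intended, the estimate and interval are still missing.

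An estimate from the 8 and 8 completers would have a 95% half-width of about 1.07 SD unadjusted, or about 1.0 to 0.8 SD adjusted. An observed difference of zero would therefore remain compatible with roughly 0.8 to 1.1 SD in either direction. These figures assume a two-sided 0.05 level and, for the adjusted range, a correlation of 0.3 to 0.7. The 0.42 SD at 45 per arm further assumes equal allocation, which the protocol does not state. Non-inferiority within any usual margin is unlikely to be shown, though not impossible.

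**What to change.** In the SAP's planned analyses:

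1. Add the CCT minus TF-CBT difference in PTSD-RI total score at month 3, adjusted for the baseline score, for the child and parent versions separately, each with a 95% confidence interval.
2. Label the contrast exploratory. The SAP is dated 9/18/20, after the July 2020 end scheduled in protocol sections 2.g and 5.m, and it already gives completer counts.
3. State that a non-significant difference will not be read as equivalence or non-inferiority, and that separate within-arm results will not be used to compare the therapies.

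The third item alone would not be enough, because it leaves the motivating comparison without an estimate.

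The cost is a few sentences and one contrast per PTSD-RI version from data already collected. The downside is an imprecise extra result and giving up any claim that CCT is as good as TF-CBT.
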